11.4.2 Primary Analysis

In this pilot trial, feasibility and safety of the robotic platform in bariatric surgery will be assessed.

For the primary outcome (safety), following variable will be reported: intraoperative complications, postoperative morbidity, and postoperative mortality.

For the secondary outcomes (feasibility) following variable will be analysed: Docking time, Operation time, conversion rate, length of hospital stay and rehospitalisation rate.

Baseline characteristics and perioperative data will be presented as medians (IQ-range) for continuous variables or frequencies (percentages) for categorical variables.

Operation and docking time will be represented as a visual graphic with its evolution over time.

Descriptive statistics, graphs will be performed with SPSS Version 25.

For the primary outcome (safety), the analysis will be done after the 30-day follow-up of the last participant.

For the secondary outcome (feasibility), the analysis will be done after the 30-day follow-up of the last participant.

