Measurements and procedures:	
Eligible patients for bariatric surgery are included into the study during the outpatient consultation used to plan the bariatric procedure (incl. signature of the informed consent + collection of clinicopathological data*).
 
Perioperative data** are collected after the operation, on the hospital release day and during the postoperative consultation 30 days after surgery.
 
*Patient's clinicopathologic characteristics: age, sex, ASA score, BMI, previous abdominal surgery (laparoscopic, laparotomy), comorbidity (cardiovascular, respiratory, renal, neurological, psychiatric disease, other relevant disease).
 
**Perioperative data: type of procedure, docking time, operation time, intraoperative complication (bleeding, organ lesion, procedure interruption), conversion, postoperative complication at 30 day postoperatively (Clavien-Dindo Classification + type of complication: postoperative bleeding, anastomotic or staple line leakage, surgical site infection, cardiovascular complication, respiratory complication, thromboembolic complication, renal complication...) and need for re-intervention. Length of hospital stay and rehospitalisation rate at 30-day postoperatively.

Intervention:	The bariatric procedure will be done using the Senhance™ Surgical System. It is a robotic technology developed by Asensus Surgical aimed to assist in the accurate control of laparoscopic instrument for visualization and manipulation of tissue (grasping, cutting, blunt and sharp dissection and suturing) in laparoscopic and thoracoscopic surgery. This technic is provided with haptic feedback, eyetracker system, 3mm instruments and 3-dimensional visualization. The product bears a CE mark.
Control intervention (if applicable):	Not applicable
Number of subjects with rationale:	Treatment group: 39 patients should be included into the study as calculated for the Simon's two stage design of the study
Duration of the investigation:	12 months
Investigation schedule:	01.12.2021 First-Participant-In (planned) 30.11.2022 Last-Participant-Out (planned)
Investigator(s):	[name], Leitender Arzt Bariatrische Chirurgie Klinik für Viszerale Chirurgie und Medizin Inselspital – Universitätsspital Bern [name] [contact] [contact]
Investigational Site:	Single centre, Inselspital (University hospital Bern)

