Statistical considerations:	The primary endpoint of our study is the safety of this new robotic platform in bariatric surgery. Therefore our study is designed as a single arm, two-stage phase II study with a stopping rule for safety using the Simon's two-stage design. Considering that conventional laparoscopic bariatric procedures present a complication rate around 10%, we set the maximum acceptable threshold of complication at 25%. Type I error is assumed to be 0.05 and Type II error 0.8. Therefore a sample size of 39 patients is needed with an interim analysis at 22 patients. The stopping rule is 5 or more events at the interim analysis and robotic surgery is considered safe if less than 6 events occurred. Baseline characteristics and perioperative data will be presented as medians (IQ-range) for continuous variables or frequencies (percentages) for categorical variables. For statistical analysis SPSS Version 25 will be used. The docking time and operation time will be represented as a visual graphic with its evolution over time.
Compliance statement:	This investigation will be conducted in compliance with the CIP, the current version of the Declaration of Helsinki, ISO14155, ICH-GCP (as far as applicable) as well as all national legal and regulatory requirements.

ABBREVIATIONS

Provide a list of abbreviations used in the CIP – to be completed/adapted

AE Adverse Event

ADE	Adverse Device Effect
ASA score	American Society of Anesthesiology
ASADE	Anticipated Serious Adverse Device Effect
ASR	Annual Safety Report
BMI	Body mass index
CA	Competent Authority (e.g. Swissmedic)
CEC	Competent Ethics Committee
CIP	Clinical investigation plan
ClinO	Ordinance on Clinical Trials in Human Research (in German KlinV, in French Oclin, in Italian OSRUM)
ClinO-MD	Ordinance on Clinical Trials with Medical Devices (in German: KlinV-Mep, in French: Oclin-Dim, in Italian: OSRUM-Dmed)
CRF	Case Report Form (pCRF paper CRF; eCRF electronic CRF)
DD	Device Deficiency
DMC / DSMC	Data Monitoring Committee, Data Safety Monitoring Committee
Ho	Null hypothesis
H1	Alternative hypothesis
HRA	Federal Act on Research involving Human Beings (in German: HFG, in French: LRH, in Italian: LRUm)
IB	Investigator's Brochure
ICF	Informed Consent Form
ICH-GCP	International Council for Harmonisation – guidelines of Good Clinical Practice
IFU	Instruction For Use
ISF	Investigator Site File
ISO	International Organisation for Standardisation
ITT	Intention to treat

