6.2.3 Other methods for minimising bias

For minimization of selection bias, all consecutive patients eligible for laparoscopic bariatric surgery and meeting the inclusion criteria will be offered to participate in this study and will be prospectively included in the study.

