8. CLINICAL INVESTIGATION INTERVENTION

8.1 Identity of the medical device under investigation

8.1.1 Experimental Intervention (medical device)

We plan to perform Sleeve gastrectomy, Y-Roux Gastric bypass and Omega-loop gastric bypass with the Senhance™ Surgical System.

According to our approach in laparoscopic bariatric surgery access to the intraabdominal space will be performed with a 12 mm self-cutting optical trocar under direct vision, which offers the visualization of different tissue layers to guarantee a safe entry to the intra-abdominal space. Pneumoperitoneum will be set to 12-15 mmHg. The following trocars will be placed under visual control. Placement and introduction of the robotic arm will be done by a trained surgeon or a trained surgical nurse under the supervision of the primary surgeon.

The planned procedure will be performed with the Senhance™ robotic system and, if required, assisted laparoscopically, for example, for the use of suction/irrigation devices, endoscopic staplers or for better exposure (liver retractor).

At the end of the procedure, the trocars will be retracted under visual control, and the skin closed with a skin stapler. As usual, in bariatric surgery in our center, abdominal wall closure will not be performed.

The Senhance™ robotic system will be used according to the manual instruction (see below). The operator and the assistant at the table have been trained before using the robot by Asensus Surgical (2 days of dry lab and 1 day of wet lab). A representative of Asensus Surgical is also present during the intervention in the operating room to supervise and offer technical support if necessary.

From Senhance Surgical System User Manual:

"The Senhance Surgical System is intended to assist in the accurate control of laparoscopic instruments for visualization and endoscopic manipulation of tissue including grasping, cutting, blunt and sharp dissection, approximation, ligation, electrosurgery, suturing, mobilization, retraction, and sealing of vessels up to and including 5 mm in diameter in laparoscopic and thoracoscopic surgery. The system is indicated for adult and pediatric use. It is intended for use by trained physicians in an operating room environment in accordance with the Instructions for Use. Use of the device is limited to patients with a weight equal to or above 10 kg, who are suitable to be subjected to a conventional endoscopic technique.

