10.4.1 Foreseeable adverse events and anticipated adverse device effects

Possible adverse effects specific to the Senhance™ Surgical System are the same as traditional laparoscopic surgery. Due to a learning curve, the operation time will probably be, in the beginning,

longer than in general laparoscopic bariatric surgery.

Mortality at less than 30 days after a Sleeve Gastrectomy is estimated at 0.29% (95% CI : 0.11 to 0.63%) and for Roux-en-Y gastric bypass at 0.38% (95% CI: 0.22-0.59%). The reoperation rate after a Sleeve Gastrectomy is estimated at 2.96% and for Roux-en-Y gastric bypass at 5.34%. The postoperative complication rate after a Sleeve Gastrectomy is estimated at 8.9% and for Roux-en-Y gastric bypass at 12.0%. [23]

The most common complications after bariatric surgery and their treatments are:

- anastomotic or staple line leakage → endoscopic or surgical closure / drainage
- postoperative bleeding → blood transfusion, coagulation optimization, reoperation
- pulmonary complications → antibiotics, invasive ventilation
- thromboembolic complications → anticoagulation
- surgical site infection → local treatment, VAC therapy, antibiotics

We expect no adverse events specifically related to Senhance™ Surgical system. Expected possible adverse events are the same as in traditional laparoscopic bariatric surgery. For other robotic platforms, literature reports a similar rate of postoperative morbidity and mortality between robotic and laparoscopic bariatric surgery [9, 24].

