11.4 Planned Analyses

11.4.1 Datasets to be analysed, analysis populations

In the absence of contraindication (see exclusion criteria below) we will include consecutive patients which are eligible for bariatric surgery according to the SMOB-Criteria and having a robotic bariatric operation (including Sleeve gastrectomy, Y-Roux gastric bypass, Omega-loop gastric bypass) at our Adiposity Center at the Inselspital, University Hospital Bern, Switzerland.

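### The planned graph of operation time over time does not distinguish the three procedures, so a shift in case mix could imitate or hide a learning curve

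*Protocol*

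**What the plan says.** Section 11.4.2 of the protocol states: "Operation and docking time will be represented as a visual graphic with its evolution over time". The statistical considerations in the synopsis repeat this: "The docking time and operation time will be represented as a visual graphic with its evolution over time". Neither sentence mentions type of procedure.

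The analysis population in section 11.4.1 is a single group of patients "having a robotic bariatric operation (including Sleeve gastrectomy, Y-Roux gastric bypass, Omega-loop gastric bypass"), and section 8.1.1 confirms the three operations: "We plan to perform Sleeve gastrectomy, Y-Roux Gastric bypass and Omega-loop gastric bypass". Inclusion is consecutive. Under section 6.2.3, "all consecutive patients eligible for laparoscopic bariatric surgery and meeting the inclusion criteria will be offered to participate in this study". No quota, stratum or order of procedures is stated.

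Type of procedure is recorded. The perioperative data listed in the synopsis begin with "type of procedure, docking time, operation time, intraoperative complication".

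Sections 3.5 and 6.1 say that the team expects still to be in the learning curve when the trial starts. Section 10.4.1 ties this to operation time: "Due to a learning curve, the operation time will probably be, in the beginning", longer than with conventional laparoscopy. Docking time is not mentioned there.

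Section 11.4.3 (secondary analyses) is marked not applicable.

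**The concern.** The graph is the only planned look at change over time, so it is where a reader will look for the learning curve that the protocol anticipates. A plot of operation time against calendar time or case order shows two things together: how quickly the team performs a given operation, and which operations it happened to perform early and late. If one procedure takes longer than another and its share changes during the trial, the second component moves the curve without any change in skill.

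A falling share of the longer procedure would look like learning. A rising share could flatten or reverse a real gain. The variable needed to tell these apart is collected, but no planned analysis of the times uses it. At stake is the reading of one secondary feasibility outcome. The safety conclusion is not affected.

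**Working it through.** The protocol gives no figure for this graph, so there is nothing of its own to reproduce. It also gives no operation times by procedure and no expected mix. From the protocol come the 39 patients (section 11.2), the three procedures (8.1.1, 11.4.1), consecutive inclusion (6.2.3) and the expectation of learning in operation time (10.4.1). All minutes and shares below are assumptions. For simplicity, the two bypass types are treated as one group with a longer operation time than the sleeve.

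**Step 1. Size of the shift.** Let d be the difference in mean operation time between bypass and sleeve, and Δp the change in bypass share between early and late cases. With no change in skill:

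shift in pooled mean = d × Δp

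- 30 min × 0.20 = 6 min
- 45 min × 0.40 = 18 min
- 60 min × 0.40 = 24 min

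**Step 2. Does chance alone move the mix?** Suppose a constant 50/50 mix, and compare the first 19 cases with the last 20. The SD of the difference in bypass share is

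√[0.25 × (1/19 + 1/20)] = 0.16

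One SD of chance variation in mix then shifts the early-to-late difference in mean time by 0.16 × 30 ≈ 5 min to 0.16 × 60 ≈ 10 min. No deliberate ordering of cases is needed.

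**Step 3. Simulation of a stronger drift.** The simulation had 39 consecutive operations, a linear drift in bypass share, an assumed SD of 20 min and 1,000 runs per scenario. Results are the mean first-to-last change in fitted time.

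| Scenario | Gap 15 min | Gap 30 min | Gap 45 min | Gap 60 min | Trend adjusted for procedure |
|---|---|---|---|---|---|
| No learning, bypass share falls from 80% to 20% | −9 | −18 | −27 | −35 | about 0 |
| True gain of 20 min, bypass share rises from 20% to 80% | −12 | −2 | +7 | +17 | about −20 |

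These agree with step 1. For a 30-minute gap, 30 × (−0.60) = −18 in the first row, and −20 + 30 × 0.60 = −2 in the second.

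**Step 4. When there is no distortion.** With a constant expected 50/50 mix, or with no time gap between procedures, the pooled trend was right on average (about 0 with no learning, about −20 with a true gain of 20 min). A systematic distortion needs both a gap and a drift. Under a constant expected mix, the chance imbalance in step 2 can still affect a single trial.

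**The case against.** The strongest reply is that the protocol does not say the procedures will share one curve. It says only that the times will be shown graphically over time, and marking by procedure is a display detail that a statistical analysis plan, not available here, could settle. Much of this stands. A reader might infer that the protocol has decided to pool the procedures, but the text is silent and supports only the statement that the graph does not distinguish them. What remains is that the protocol specifies this graph in two places and names no breakdown in either, while expecting learning in operation time.

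Three further readings are tempting and not supported:

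- **Docking time.** A reader might extend the point to it. Nothing in the protocol suggests that docking time depends on the procedure, and section 10.4.1 links learning to operation time only.
- **Main evidence on feasibility.** Sections 4.3 and 5.2 list five feasibility outcomes: docking time, operation time, conversion, length of stay and rehospitalisation. Section 5.2 treats the intraoperative ones as indirect information. Section 11.4.2 also plans medians with interquartile ranges.
- **Easier cases first.** A reader might assume that harder procedures are added later. The protocol plans consecutive inclusion and says nothing of the kind, and bariatric use of the robot began on 28.06.2021, about five months before the planned start. The point does not need this premise, because the mix can vary by chance.

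It is also fair to say that the minutes are wholly assumed and cannot show that the distortion would be material in this trial.

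**Conclusion.** The point holds as a minor one about operation time. As written, the planned graph cannot separate learning from a change in the mix of procedures. Under the assumptions in step 1 of the working, the apparent shift is 6 to 24 minutes. Chance variation at an assumed 50/50 mix contributes about 5 to 10 minutes at one SD. These figures rest on assumed time gaps and shares. If the procedures take equally long, or the realised mix stays stable, there is no distortion.

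The consequence is limited to the interpretation of a descriptive display of a secondary feasibility outcome. The stopping and success rules in section 11.2 count complications and are untouched.

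**What to change.** In section 11.4.2 and in the statistical considerations of the synopsis, state that operation time will be plotted by case order with each procedure shown by its own symbol or panel, and that median (IQR) operation time will be reported by procedure. Marking docking time in the same way is only a precaution. A regression of time on case order and procedure is optional and not needed in a descriptive pilot.

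The cost is one sentence in each place. No new data, patients or visits are required, because procedure type is already recorded. The one drawback is that a rare procedure will have few points. Symbols on a single graph largely avoid this, since all 39 cases stay visible together.

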11.4.3 Secondary Analyses

Not applicable

11.4.4 Interim analyses

To guarantee the procedure's safety, the intraoperative and postoperative complications, as well as the postoperative mortality, will be analyzed after inclusion of 22 participant and will be presented as frequencies (percentages). The analysis will be done by the Sponsor-Investigator. If there are 5 or more events, the Sponsor-Investigator will terminate the study for safety.

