2.7 Patient Information and Informed Consent

The Investigators explain to each subject the nature of the investigation, its purpose, the procedures involved, the expected duration, the potential risks and benefits and any discomfort it may entail. Each subject is informed that the participation in the investigation is voluntary and that he/she may withdraw from the investigation at any time and that withdrawal of consent will not affect his/her subsequent medical assistance and treatment. The subjects are informed that he/she can ask any question, and consult with family members, friends, their treating physicians or other experts before deciding about their participation in the investigation. Enough time is given to the subjects

The subjects are informed that authorised individuals other than their treating physician may examine his/her medical records.

All subjects are given a subject information sheet and a consent form describing the investigation and providing sufficient information for the subjects to make an informed decision about their participation in the investigation. The enrolment will be performed during the outpatient consultation used to plan the bariatric procedure. The bariatric procedure will be done at least five days after this consultation, and patients can until then retract their consent if they do not want to participate in this study. No participant will be included in an emergency situation.

The formal consent of a subject, using the approved consent form, is obtained before the subject is submitted to any investigation procedure.

The subject should read, understand, and voluntarily agree before signing and dating the informed consent form, and is given a copy of the signed document. The consent form is signed and dated by the subject and the Co-Investigators (or her/his designee). The signed consent form is retained as part of the investigation records.

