5. CLINICAL INVESTIGATION OUTCOMES

5.1 Primary Outcome

The primary outcome will evaluate the safety of the use of the Senhance™ Surgical System in bariatric surgery.

Intraoperative complications such as bleeding, organ lesion, and procedure interruption will be monitored during the operation and reported postoperatively.

Postoperative complications and re-operation will be reported at discharge and at the 30-days follow up control. Complications will be classified according to its gravity by the Clavien-Dindo classification and by its type (postoperative bleeding, anastomotic or staple line leakage, surgical site infection, cardiovascular complication, respiratory complications, thromboembolic complication, renal complication...).

30-day postoperative mortality (= Clavien Dindo grade V) will be reported at discharge and at the planned 30-day-checkup.

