6. CLINICAL INVESTIGATION DESIGN

6.1 General clinical investigation design and justification of design

Our study will evaluate the feasibility and safety of Senhance™ Surgical System in bariatric surgery at a single center. Therefore we plan to perform a prospective open observational single-center study with the advantage of less bias and confounding factors than in a retrospective study. To achieve a reasonable number of participants and to minimize selection bias we plan to offer robotic operation to all eligible patients. A randomized controlled trial with conventional laparoscopic is not yet feasible as we have to evaluate the feasibility and safety of this procedure first, as we recently introduced it in our centre.

The robot was introduced in June 2021 in our clinic and the first bariatric operation was performed on 28.06.2021. Due to a delay of our application to the CEC because of the new application procedure for medical devices, the approval for our study will come after the first operated patients. Nevertheless, deduced from other teams evaluating robotic operations we believe to still be in the learning curve at the beginning of the study.

No blinding is possible in our study. We plan to include 39 participant in our study which will be operated with our robot. The inclusion period will last 12 months and the follow-up 30 days.

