9.3 Procedures at each visit

9.3.1 Peroperative consultation

All patients where bariatric surgery is indicated and desired are seen at this consultation to plan the operation. During this visit, and for those who meet the inclusion criteria, the possibility of participating in the study will be discussed. The patient will receive oral and written information about the study. If the patient meets the inclusion criteria for the study and is willing to participate, he will be included.

The operation will be planned and explained to the patient. A consultation with the anesthesiologist will be organized.

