10.4.2 Reporting of Safety related events

Reporting to the Sponsor:

All SAEs, device deficiencies and health hazards that require measures are reported to the Sponsor-Investigator by the Co-Investigators (or authorized designee) within 24 hours after becoming aware of the event. Device deficiencies are assessed regarding their potential to lead to an SAE. DD are assessed regarding their potential to lead to an SAE.

Pregnancies

On the day of the operation each female participant that can be pregnant (except hysterectomy, postmenopausal) will have a pregnancy test. If the test is positive, the operation will be reported and the participant excluded from the study.

Reporting of pregnancies after the operation is not necessary.

Reporting to the Competent Ethics Committee:

The Sponsor-Investigator reports to the CEC promptly any serious adverse event which has a causal relation with the MD, comparator or procedure/test method or where a causal relation appears to be possible (Art. 33 ClinO-MD).

In order to ensure prompt notification, the Sponsor-Investigator may initially submit an incomplete notification.

If safety and health hazards that require measures must be taken immediately during the conduct of the investigation, the Sponsor notifies the CEC within 2 days of these measures and the circumstances which made them necessary (Art. 34 ClinO-MD).

Periodic safety reporting (Art. 35 ClinO-MD):

An Annual Safety Report (ASR) is submitted by the Sponsor-Investigator to the CEC, yearly. The ASR contains a list of all SADEs and DDs and a report on their degree of seriousness, causal relationship with the MD and procedure and on subjects' safety.

Other reporting is done according to provisions of MD vigilance as per Art. 87-90 MDR (Art. 33 abs 4.b ClinO-MD) and Art. 67 MedDO.

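### The interim safety look is triggered by inclusion of 22 participants, not by their completed 30-day follow-up, so the 5-event stop may be applied to incomplete outcomes

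*Protocol*

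**What the plan says.** Section 11.4.4 of the protocol sets the interim look: the intraoperative and postoperative complications, "as well as the postoperative mortality, will be analyzed after inclusion of 22 participant". Five or more events oblige the Sponsor-Investigator to terminate. Section 11.2 and the synopsis (Statistical considerations) place the look at 22 patients and add no follow-up condition.

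Inclusion is an event with a place in the schedule. The synopsis (Measurements and procedures) says: "Eligible patients for bariatric surgery are included into the study during the outpatient consultation used to plan the bariatric procedure". Section 9.3.1 agrees: "If the patient meets the inclusion criteria for the study and is willing to participate, he will be included". Surgery comes later (section 2.7): "The bariatric procedure will be done at least five days after this consultation".

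The outcome matures later still. Section 5.1 says: "Postoperative complications and re-operation will be reported at discharge and at the 30-days follow up control", and mortality is counted to day 30.

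For the final analysis, section 11.4.2 does state the condition: "For the primary outcome (safety), the analysis will be done after the 30-day follow-up of the last participant".

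**The concern.** The boundary of 5 events was derived for 22 patients whose outcomes are all known. The trigger in section 11.4.4 fixes only an earliest time, and at that time the most recent participants are still within their 30 days or have not yet been operated on. Their later complications are not in the count, and section 11.5 provides for no imputation. The comparison with 5 is then lenient by an amount the design did not allow for.

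This look is the only numeric safety stop before stage 2. The stops in sections 2.9 and 7.4 are discretionary, section 1.6 provides no data safety monitoring committee, and section 3.5 expects the team still to be on its learning curve when the trial starts.

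It is also unclear who belongs to the 22. Section 6.1 ties inclusion to the robotic operation ("We plan to include 39 participant in our study which will be operated with our robot"), as do sections 7.1 and 11.4.1. The synopsis and section 8.4 allow a participant to be included and then never operated on robotically, and section 11.5 says that drop-outs are not replaced. Such a participant would occupy one of the 22 places without being able to contribute a device-related event.

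**Working it through.** **Inputs from the protocol.** Expected complication rate 10%, unacceptable rate 25%, type I error 0.05; interim at 22, stop at 5 or more; final at 39, success with fewer than 6 events (section 11.2). Section 11.2 prints 0.8 as the type II error; it fits the design only as power. 39 participants over a 12-month inclusion period, 30-day follow-up (section 6.1). At least 5 days from consultation to surgery (section 2.7); the schedule table shows −5/14, read here as 5–14 days.

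**The plan's own design.** With X ~ Binomial(22, p):

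- P(X ≥ 5 | 25%) = 0.6765
- P(X ≥ 5 | 10%) = 0.0621
- P(X ≤ 4 at interim and ≤ 5 of 39 at the end) = 0.0498 at 25% and 0.8024 at 10%

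The stated sample sizes and limits therefore reproduce, provided all 22 outcomes are complete at the look.

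**How many outcomes are incomplete at the earliest look?** Assuming even accrual of 39 in 365 days (one per 9.36 days):

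- counted from surgery: 39/365 × 30 = 3.2
- 5 days from inclusion to surgery: 39/365 × 35 = 3.7
- 14 days from inclusion to surgery: 39/365 × 44 = 4.7

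**Model 1, visible share.** Let c patients be complete, m be operated but not yet at day 30, and the rest not yet operated. With an assumed share v of events already visible in the m patients, the known events follow Binomial(c, 0.25) + Binomial(m, 0.25v). The chance of at least 5 is:

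| Complete + immature + not operated | v = 0.5 | v = 0.75 |
|---|---|---|
| 17 + 4 + 1 | 0.533 | 0.584 |
| 18 + 3 + 1 | 0.559 | 0.596 |
| 19 + 3 + 0 (inclusion counted on day of surgery) | 0.608 | 0.643 |

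With v = 0 the first two rows give 0.426 and 0.481. These are lower bounds only, because intraoperative and discharge data arrive promptly and serious adverse events reach the Sponsor-Investigator "within 24 hours after becoming aware of the event".

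**Model 2, event times.** Assume a share e of events falls evenly on days 0–4 and the rest evenly on days 4–30, with e from 0.25 to 0.75 and a delay of 0, 5, 9 or 14 days from inclusion to surgery. Each of the 22 then has event probability 0.25 × (share of events elapsed by the look). Convolving the 22 gives P(stop | 25%) = 0.514–0.617.

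**Effect at the end of the trial.** Late events among the first 22 still count at 39. Across both models the probability of declaring safety is 0.0500–0.0506 at 25% (design 0.0498) and 0.804–0.807 at 10% (design 0.802). P(stop | 10%) is 0.033–0.055 (design 0.062).

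**Expected inclusions at a true 25% rate.** For one early look, 39 − 17 × P(stop): with 0.617 this is 28.5, with 0.514 it is 30.3. With the look held on complete outcomes and enrolment paused, 39 − 17 × 0.6765 = 27.5. Without a pause, but stopping when a fifth event among the 22 becomes known, 22 + Σ (j = 23 to 39) P(fewer than 5 known events among the first 22 when the j-th is included) = 27.5–27.7.

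**The case against.** The wording does not order an early look: it is a lower bound, and an investigator may wait. The quantities named for analysis are defined to day 30, so a sympathetic reader could take the condition as implied, and section 12.3 attaches a monitoring visit to the interim, which suggests an organised step rather than an instant count. In Model 2, a look 14 days after the 22nd inclusion already gives 0.59–0.67, and 21 days after gives 0.62–0.67. This stands as a limit on the size of the problem. It does not supply the missing condition: section 11.4.2 states it for the final analysis, and a mandatory safety rule should not depend on someone choosing to wait.

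Second, the schedule table and section 9.3.2 put the eligibility check on the day of surgery, and section 7.1 makes the Senhance operation an inclusion criterion. On that reading all 22 have been operated on, and the chance of stopping is 0.608–0.643 in Model 1 and 0.586–0.617 in Model 2. The loss is smaller but remains.

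Third, accrual pattern, visible share and event timing are assumptions the protocol does not supply. That is correct, and is why ranges are given.

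Fourth, stopping at the fifth known event might look like continuous monitoring added to a one-look design. It is not: within a fixed set of 22, the fifth event is reached if and only if the completed count is at least 5, so the stopping probability stays at 0.677.

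**Conclusion.** The concern holds. The stated trigger permits the mandatory stop to be judged on immature outcomes. At the earliest permitted time, the chance of stopping at a true 25% rate falls from 0.677 to about 0.51–0.64, a loss of roughly 3 to 16 percentage points. The range rests on even accrual, 0–14 days from inclusion to surgery, and the assumed visibility or timing of events. It narrows if the look is in practice held later.

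The damage is confined to early protection. At a true 25% rate it amounts to about 1 to 3 additional expected inclusions (28.5–30.3 against 27.5–27.7), with the final false-safe probability essentially unchanged. The missing condition is certain from the text; the size of its effect is less so. It should be fixed but does not undermine the final test.

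**What to change.** Amend sections 11.2 and 11.4.4 and the synopsis to say that:

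1. the interim set is the first 22 participants operated with the Senhance system;
2. the decision to continue is made only when all 22 have completed 30-day follow-up;
3. the existing limit of 5 is kept and counts as met as soon as a fifth event among these 22 is known.

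The cost is two or three sentences in three places. The sample sizes and the boundary do not change. If enrolment pauses, the wait is about 5–6 weeks from the 22nd inclusion (35–44 days). If it continues, up to about 3–5 participants may be included in the meantime, but expected inclusions at a true 25% rate are still lower than under the early look. There is a small price at a true 10% rate: the chance of an interim stop returns to its design value of 0.062 (from 0.033–0.055), and power returns to 0.802 (from 0.804–0.807).
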